5.1. Study Population and Eligibility

All patients who are scheduled to undergo an EUS-FNA procedure of a PCL by a study Investigator will be offered the opportunity to enroll in the study (see **Section 8.2** below). A count of such consecutive patients will be kept at each participating center from the time the center is enrollment-ready to when enrollment is closed for the center. Subjects will be asked to sign an Informed Consent form (ICF) before any study-specific tests or procedures are performed. Pregnant women will be excluded as per routine clinical care.

5.2. Inclusion Criteria

1. Pancreatic cystic lesion measuring 13mm or greater in largest diameter.*
2. Indicated for EUS evaluation of the PCL including EUS-FNA.
3. Age 18 years of age or older.
4. Willing and able to comply with the study procedures and provide written informed consent form to participate in the study.

NOTE: * In a multilocular cyst, the largest locule should measure 13mm or greater in its largest diameter.

5.3. Exclusion Criteria

1. Cysts in which FNA is not indicated based on review by the clinician, including potential concern of blood vessel location relative to the cyst.
2. Requirement for anticoagulation using clopidogrel, warfarin, or other long acting antiplatelet agents (with the exception of aspirin) that cannot be safely stopped according to institutional guidelines.
3. Standard contraindications for EUS.

4. Known pancreatic pseudocyst.
5. Pregnancy.

6. Study Devices

Three versions of the Expect™ Endoscopic Ultrasound Aspiration Needle will be used in this study. The Expect™ Needle is a market-approved device designed to sample targeted sub mucosal and extramural gastrointestinal lesions through the accessory channel of a curvilinear echoendoscope.

Study devices are labeled on the box and inner pouch and include name of the legal manufacturer, device name and dimensions, lot number, and expiration date. Device labeling will be provided in local language(s) as per national regulations.

For a detailed description of the Expect™ Endoscopic Ultrasound Aspiration Needle, please reference the Directions for Use (DFU) included in each device package.

Devices with the specifications outlined in **Figure 2** below will be used in the study:

Figure 2 – Device Chart

Device Name	Delivery System Working Length	Needle Size	Needle Diameter	Needle Length
Expect™ Endoscopic Ultrasound Aspiration Needle	137.5 cm to 141.5 cm adjustable	- 22 G - 19 G - 19 G Flex	- 0.72 mm - 1.10 mm - 1.14 mm	0 cm to 8 cm adjustable

7. Study Procedures

Endoscopic ultrasound will be performed using standard linear sector scanning EUS equipment (e.g., Olympus, Pentax, or Fujinon). Study procedures will be followed as outlined in the sections below.

7.1. Antibiotic Treatment

All patients will be given broad spectrum antibiotics such as fluoroquinolone for at least 3 days starting on the day of the EUS-FNA procedure.

7.2. Needle Puncture and Aspirate Requirements

The following procedural rules will be followed:

- a. Initial needle puncture with stylet in place (with time stamp). Remove stylet and apply 10cc suction. If no aspirate visible in syringe lumen after 5 seconds of suction: reposition needle and re-apply suction. If no aspirate after 5 seconds of suction- lesion classified as FNA failure. Switch to salvage method.

- b. If aspirate visible within syringe lumen, hold suction until no additional material accumulated for 10 seconds. If cyst completely collapses, note final time stamp. If cyst is not completely collapsed, then repositioning is allowed until all cyst locules have been punctured, and no additional fluid is obtained for 10 seconds. Note final time stamp. If cysts is not completely collapsed after attempts, above, note final maximal and perpendicular diameter.
- c. In case of a multi-compartment, loculated lesion, all locules accessible with the same needle pass will be aspirated, with priority to the largest locule. In cases where a locule is positioned in front of another along the axis of the needle, the one most proximal to the needle tip should be fully aspirated before accessing the locules located in a more distal position.
- d. In the event that cyst components cannot be reached without repuncture, remove needle completely from cyst (note time stamp for pass completion). Repuncture for pass 2 (or more) as needed until criteria (see "b" above) for complete aspiration or failure is met.
- e. If maximal cyst diameter is > 5mm after efforts described in "b" above, cyst aspiration is considered "failed." Switch to salvage method (19 Flex, if first method was not 19 Flex).

7.3. Salvage Aspiration

In case of inability to access the PCL or to attain complete cyst aspiration, a salvage aspiration procedure, or a repeated attempt to aspirate the PCL with another needle, should be performed.

Patients randomized to Arm 1 (19G Flex) should undergo a salvage procedure with a 22 G or 19 G needle (needle choice at discretion of physician); patients randomized to Arm 2 (22 G) and Arm 3 (19 G) should undergo a salvage procedure with a 19 G Flex needle. Salvage procedure will follow the needle puncture and aspirate requirements guidelines outlined in **Section 7.2** above.

7.4. Post-Procedure Handling of Cyst Aspirate

- a. Record final cyst maximum diameter and perpendicular diameter.
- b. Record total volume of cyst aspiration by suctioning all material, including what is in the needle lumen, into the syringe, inverting it, and removing air.
 - If sample volume is > 3cc, send 2cc to chemistry laboratory for CEA. Send remainder to cytology lab.
 - If sample volume is < 3cc, divide the sample into two aliquots guided by volumetric requirements of the local cytology and chemistry labs.
 - Sequential portions of the aspirate will be used for the two assays as follows:
 - o First aliquot (preferably at least 1cc) – Cytology
 - o Second aliquot (preferably at least 1cc) – CEA
 - o All remaining fluid is to be added to the first aliquot and sent for cytology

- In case the total aspirate volume is insufficient to satisfy local cytology and chemistry lab requirements, then the aliquot order outlined above should be used to prioritize which subset of assays will be performed.
- In cases in which the aspirate volume is more than 1 cc but less than 3 cc, the first cc should be sent for cytology and the remainder should be sent for CEA. Some laboratories may have the ability to perform CEA assays on less than 1 cc of fluid for assay.
- In cases in which the aspirate volume is less than 1 cc, the aspirate will nevertheless be sent for cytology.

7.5. Adverse Event Assessment

- Immediate Adverse Event assessment: Assessment for immediate complications during the procedure and prior to discharge (approximately 2hrs post-procedure) or planned hospital observation transfer will be done and will be recorded on the *Adverse Event (AE) CRF*.
- Delayed Adverse Event assessment: Assessment for delayed complications will be done by telephone at 30 days (\pm 5 days) and will be recorded on the *AE CRF*. If a scheduled office visit is made during the same time window, it may substitute for the telephone call. If surgery or other major intervention (e.g., ERCP, other invasive biopsy) is performed prior to 30 days, events will be censored at the date of the procedure.

Adverse event details including definitions, types, and reporting requirements are provided in **Section 10**.

8. Study Visits

8.1. Visit Schedule and Data Collection

The visit and data collection schedule is outlined in **Figure 3** below.

Figure 3 – Visit and Data Collection Schedule

Procedure/Assessment	Screening, Enrollment, Baseline	Procedure	30 Day Follow -up Visit (\pm 5 days)	Long Term Clinical Follow-Up Chart Review (Up to 24 months from Procedure)
ICF	X			
Eligibility Criteria Assessment	X			
Demographics	X			
Medical History	X			X
Lesion Location	X			X
Randomization	X			
Lesion Characteristics		X		X
EUS-FNA Procedure Details (including Needle Use and Times)		X		
Aspirate Characteristics		X		
Salvage EUS-FNA Procedure (if applicable)		X		
Adverse Events Assessment		X	X	
Additional Fluid Testing Results (if applicable)				X
Surgical Pathology (if applicable)				X

8.2. From Screening to Baseline

8.2.1. *Screening and Informed Consent*

On an all-comer basis, Investigators will keep a count of the number of patients to whom study participation was offered (see also **Section 5.1** above). No study-specific testing will be conducted before the subject has signed an Informed Consent Form (ICF). The ICF is study-specific and must be approved by the study Institutional Review Board (IRB)/Ethics Committee (EC) (see also **Appendix B.2** below). Study personnel should explain that even if a subject agrees to participate in the study and signs the ICF, the inclusion/exclusion criteria may demonstrate that the subject is not a suitable candidate for the study.

8.2.2. Enrollment

Patients who signed the ICF, met all inclusion criteria, and met none of the exclusion criteria will be considered enrolled. A *Screen Failure/Enrolled Log* will be maintained of patients who signed the ICF but did not satisfy enrollment criteria.

Only enrolled patients will be randomized and count toward the enrollment ceiling.

8.2.3. Baseline

Patient information will be collected on the *Baseline CRF* pertaining to:

- Demographics
- Medical History
- Lesion Location (head/uncinate, body, tail)

8.2.4. Randomization

Enrolled patients will be assigned to the 19G Flex, 22 G or 19 G Arm in a 2:1:1 ratio by randomization schedules which will be computer-generated using a pseudo-random number generator. An Interactive Web Response System (IWRS) will be utilized.

Randomization will be stratified (block randomization) by the following strata:

- Investigational center
- PCL location: head/uncinate, other

8.3. Procedure

8.3.1. Lesion Characteristics

The following lesion characteristics will be assessed by EUS prior to the start of the FNA procedure and will be recorded on the *Procedure CRF*:

- a. Cyst size (maximal diameter, and cross-sectional diameter)

NOTE: In the case of a multilocular cyst, size will be measured both as the aggregate size of all cyst locules and the long and short perpendicular axis of the largest locule.

- b. Number of locules (1, 2, 3, 4, 5, 6-10, > 10)
- c. Presence of visible mucin (floating, or mobile filling defects)
- d. Presence of mural nodule (non-mobile filling defect) and size
- e. Presence of solid components
- f. Presence of distinct PCL wall
- g. Connectivity to pancreatic duct
- h. Maximal pancreatic duct diameter

An EUS image of the patient's PCL will be saved during the procedure.

8.3.2. *EUS-FNA Procedure*

The EUS-FNA procedure will be carried out in line with the guidelines provided in **Section 7** above, and the following data will be collected and recorded on the *Procedure CRF*:

- a. Route of access (gastric, duodenal, esophageal)
- b. Ease of insertion of EUS-FNA needle through echoendoscope
- c. Ability to reach target lesion
- d. Ability to penetrate into target lesion
- e. Quality of needle visualization
- f. Number of needle passes
- g. Ease of removal of EUS-FNA needle from echoendoscope
- h. Aspirate characteristics and adequacy of aspirate volume to perform two assays (cytology and CEA)
- i. Adverse Event assessment during procedure and through 2 Hours Post-Procedure or discharge from endoscopy unit

8.4. **Cytology and Chemistry Results**

The results of cyst aspirate cytology and CEA assessments will be provided by the cytology and chemistry labs and will be recorded on the *Cytology and Chemistry Results CRF*. Results will be categorized as follows⁴ and will be used for determination of Disease State per EUS-FNA:

- Cytology
 - Bland PAS +
 - Mucinous
 - Pigmented histiocytes
- CEA (ng/mL)
 - < 0.5
 - > 0.5 and < 200
 - > 200

8.5. **30-Day Follow-up**

The post-procedure 30-day Follow-up Visit will be conducted over the telephone. The visit window allows for this visit to occur anytime from 25 days to 35 days post procedure. Patients will be assessed for potential adverse events that might have occurred from discharge until 30 days post-procedure. AE information will be recorded on the *Adverse Event CRF*.

End-of-Study information including information about loss to follow-up or any other circumstances that might have led to the patient's study participation ending will be collected on the *End of Study CRF*. A subject will be considered lost to follow-up after 3 documented attempts of contact by study staff.

Protocol deviations will also be documented throughout the study.

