9.1. Study Hypothesis and Sample Size Calculation

Sample size was calculated based on assumptions for the primary endpoint as well as for secondary endpoint c):

9.1.1. *Primary endpoint considerations:*

The study hypothesis states that for either of the 19 G Flex and 19 G Arms, the volume of actual aspirated cyst fluid as a ratio (%) of estimated maximal volume is superior by at least 10% compared to that of the 22 G Arm.

The study investigators provided the following experience-based estimate of the primary endpoint (aspirate volume as % of max volume based on EUS image of the cyst):

Figure 4 – Hypothesis Generating References (Primary Endpoint)

Site Investigator	Mean Volume Ratio (%) for 19G and 19Flex needles	Mean Volume Ratio (%) for 22G needles
Investigator 1	80%	50%
Investigator 2	90%	70%
Investigator 3	90% Unilocular cysts, 50% Multi-locular	80%

	cysts, 80% Blended mean	
Investigator 4	90%	90%
Investigator 5	90%	50%
Investigator 6	85%	65%

From the above table, bootstrap method with 10,000 resamples yielded an estimated mean of 67.44% and standard deviation of 15.29% for 22G, and a mean of 85.9% and standard deviation of 4.67% for 19G/19G Flex.

The assumption was made that the mean of the “control group”, namely the 22G arm, will be 67% with a standard deviation of 15.29%.

Two null hypotheses are made:

- H_{01} : Mean volume ratio of 19 G Flex Arm and 22 G Arm are the same
- H_{02} : Mean volume ratio of 19 G Arm and 22 G Arm are the same

The alternative hypothesis is:

- H_1 : Mean volume ratio of 19 G Flex/19G Arm is superior to 22 G Arm

If 50 patients are enrolled in the 19 G Flex Arm and 25 patients each in the 19 G and 22 G Arm, the study will have 90% conjunctive power to detect the rejection of both null hypotheses to demonstrate superiority of the mean volume ratio of 19 G Flex Arm and 19 G Arm to that of 22 G Arm by 10% or more. Thus, a minimum of 100 patients (50+25+25=100) are required.

9.1.2. Secondary endpoint c) considerations:

The study hypothesis states that the EUS-FNA 19 G Flex needle is superior to the EUS-FNA 22 G standard and 19 G standard needles in the secondary endpoint c) measure, which requires access or adequate aspirate volume for two standard assays expected from successful EUS-FNA procedures in PCL assessment indications.

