When specific tasks are delegated by an Investigator, included but not limited to conducting the informed consent process, the Investigator is responsible for providing appropriate training and adequate supervision of those to whom tasks are delegated. The Investigator is accountable for regulatory violations resulting from failure to adequately supervise the conduct of the clinical study.

B.11 Confidentiality

All information and data sent to the Sponsor concerning subjects or their participation in this study will be considered confidential by the Sponsor. Only authorized Sponsor personnel or a Sponsor representative will have access to these confidential records. Study data collected during this study may be used by the Sponsor for the purposes of this study, publication, and to support future research and/or other business purposes. All data used in the analysis and reporting of this study will be without identifiable reference to specific subject name.

The Sponsor will keep subjects' health information confidential in accordance with all applicable laws and regulations. The Sponsor may use subjects' health information to conduct this research, as well as for additional purposes, such as overseeing and improving the performance of its device, new medical research and proposals for developing new medical products or procedures, and other business purposes. Information received during the study will not be used to market to subjects; subject names will not be placed on any mailing lists or sold to anyone for marketing purposes.

B.12 Monitoring

Regular on site monitoring by the Sponsor will not be planned during the study, but occasional visits by the Sponsor may be conducted as a measure of quality assurance. However, the study database will be monitored to ensure that data are reported in a satisfactory manner with respect to timeliness, adequacy, and accuracy. Sites will be queried in the case of any missing, incomplete or inconsistent data.

The Investigator/institution guarantees direct access to original source documents by Sponsor personnel and their designees if required during a monitoring visit or quality assurance audit.

B.13 Enrollment Controls

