### 3 ENDPOINT ANALYSIS

#### 3.1 Primary Endpoint

##### 3.1.1 Hypotheses

The primary endpoint is “Volume of aspirated cyst fluid as a function of estimated maximal volume based on pre-aspiration EUS measure of cyst diameter (s) (% aspiration of total estimated volume).”

Analysis Approach:

% aspiration of total estimated volume is calculated overall and for each arm (19 G Flex, 22 G, 19 G) and/or a combination of arms such as 19G Flex and 19G, for each and combined morphologic characteristics, and for no salvage subjects. If there is multilocular morphology, the primary endpoint is calculated for measurements of the largest locule.

Valid Data Sources:

- Procedure Form: sections “PCL Characteristics” and “Post-Aspiration Assessment”

Valid Data Points:

- Morphology: Unilocular (Pre-aspiration EUS measures)
  - Maximal diameter (long axis) (mm)
  - Perpendicular measurement (short axis) (mm)
- Morphology: Multilocular (Pre-aspiration EUS measures)
  - Measurements of the largest locule
    - Maximal diameter (long axis) of the largest locule (mm)
    - Perpendicular measurement (short axis) of largest locule (mm)
- Total volume of aspirate (Post-aspiration assessment)

Formula:

$$\% \text{ aspiration of total estimated volume} = \frac{A-B}{A} \times 100 \%$$

Volume is computed using the standard geometric formula  $\left(\frac{4}{3}\pi R^3\right)$  where R is half the long axis. The volume unit is in cc. “A” is calculated by the image during pre-procedure measurements. “B” is calculated by the image during post-procedure measurements.

Hypotheses:

$H_{0i}: \mu_i - \mu_0 \leq 0$  Versus  $H_{1i}: \mu_i - \mu_0 > 0$  for  $i=1, 2$ ;

where  $\mu_0$  is mean volume percentage of 22 G Arm,  
 $\mu_1$  is mean volume percentage of 19 G Flex Arm, and  
 $\mu_2$  is mean volume percentage of 19 G Arm.

Superiority by 10% or more is deemed clinically significant.

The multiple comparison Hochberg's step up method will be used.

The analysis population for the primary endpoint will be the Intent to Treat and Per-protocol analysis sets.

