### 3.1.2 Sample Size

The sample size was estimated based on the following assumptions:

Design parameters:

One-sided Type I Error=0.05

Multiple comparison method= Hochberg's step up

Rejection region=Right tail

Treatment parameters:

Arm	Mean volume percentage	Standard deviation	Sample size per group
22G	67	15.29	25
19G	77	4.67	25
19GFlex	77	4.67	50

Overall power:

Global (reject any  $H_{0i}$ ): 0.912

Conjunctive (reject all  $H_{0i}$ ): 0.901

Given the above assumptions, a total sample of 100 subjects will be required where 50 subjects will be in 19 G Flex arm, and 25 subjects in the 19 G and 22 G arms respectively.

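### The pre-aspiration diameter that forms the denominator of the primary endpoint is read after randomisation with no masking described; assigning the needle after that reading would remove the exposure at little cost

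*Protocol*

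**What the plan says.** Protocol 8.2.4 states that "Enrolled patients will be assigned to the 19G Flex, 22 G or 19 G Arm in a 2:1:1 ratio by randomization schedules". The follow-up schedule in the Synopsis and Figure 3 in 8.1 both place this step at baseline. The size measurements come later, at the procedure: "The following lesion characteristics will be assessed by EUS prior to the start of the FNA procedure" (8.3.1). The note in Protocol 9.3 confirms the order, since it allows exclusion criterion 1 to be recorded once a patient has been randomised and EUS has begun.

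The diameter feeds the primary endpoint in two ways that do not agree. Protocol 4.1 relates the aspirated volume to the volume estimated from the pre-aspiration diameter(s). SAP 3.1.1 uses (A−B)/A, with each volume that of a sphere whose radius is half the long axis. It says that A "is calculated by the image during pre-procedure measurements" and that B comes from the corresponding post-procedure measurement.

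On images, 8.3.1 requires only this: "An EUS image of the patient's PCL will be saved during the procedure". On oversight, Appendix B.12 says "Regular on site monitoring by the Sponsor will not be planned during the study", although it allows occasional quality visits, database monitoring and access to source documents. The only masking in either document is that of the consensus board for diagnosis (Protocol C.3, SAP 5.1.2). SAP 4.5 names stratified randomisation as the only control of systematic error.

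**The concern.** Whoever reads the diameter can already know which needle the patient will receive, and nothing in the documents prevents this. The long axis is cubed in the SAP volume, so a small reading difference becomes a larger volume difference. If readings lean differently by arm, the comparison of arms shifts without any true difference in aspiration.

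Such a lean is at least plausible. In Protocol Figure 4, four of the six investigators expected the 19 G needles to do better than 22 G by 20 to 40 points, two expected no difference (one of them on a blended mean), and none expected 22 G to do better. This does not show that a lean will occur. It does mean that expectations about the needles existed before the trial, which is when masking is useful.

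**Working it through.** **Inputs.** Design means are 67% (22 G) and 77% (both 19 G arms). The 22 G arm, in the protocol's words, "namely the 22G arm, will be 67% with a standard deviation of 15.29"; the SD in both 19 G arms is 4.67 (Protocol 9.1.1, SAP 3.1.2). Design parameters are "One-sided Type I Error=0.05" and "Multiple comparison method= Hochberg's step up". The planned difference is 10 points. The primary endpoint needs 25 (22 G), 25 (19 G) and 50 (19 G Flex) patients; endpoint c sets the actual arms at 61, 61 and 121. The minimum cyst diameter is 13 mm. The documents give no expected diameter and no reading error.

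**Reproducing the plan's figure.** The stated power is 0.912 global and 0.901 conjunctive. Simulation of 300,000 trials with unequal variances and Hochberg's procedure gives 0.915 and 0.904 (t reference), or 0.927 and 0.915 (the normal reference of SAP 3.1.3). The design inputs therefore reproduce closely.

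**Shift from a lean d on a true diameter D, at a true mean of p%.** The protocol gives no volume formula, so I use the SAP's sphere for both versions. With k = (D/(D+d))³:
- Protocol ratio: change = p × (k − 1)
- SAP percentage, B read correctly: change = (100 − p) × (1 − k)

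For D = 30 mm and d = +1.5 mm, k = (30/31.5)³ = 0.864.
- Protocol: 67 becomes 57.9 (−9.1) and 77 becomes 66.5 (−10.5).
- SAP: 67 becomes 71.5 (+4.5) and 77 becomes 80.1 (+3.1).

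Shift in points for an assumed lean of 1.5 mm in one arm (over-reading / under-reading):

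| D (mm) | Protocol, 67% | Protocol, 77% | SAP, 67% | SAP, 77% |
|---|---|---|---|---|
| 13 | −18.7 / +29.8 | −21.5 / +34.2 | +9.2 / −14.7 | +6.4 / −10.2 |
| 20 | −13.1 / +17.7 | −15.0 / +20.3 | +6.4 / −8.7 | +4.5 / −6.1 |
| 30 | −9.1 / +11.1 | −10.5 / +12.8 | +4.5 / −5.5 | +3.1 / −3.8 |
| 40 | −7.0 / +8.1 | −8.1 / +9.4 | +3.5 / −4.0 | +2.4 / −2.8 |

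The size also depends on the assumed lean. For over-reading at 30 mm and 67%, leans of 0.5, 1, 2 and 3 mm move the protocol ratio by 3.2, 6.3, 11.8 and 16.7 points, and the SAP percentage by 1.6, 3.1, 5.8 and 8.2.

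**The post-aspiration reading, SAP formula only.** At D = 30 mm and 67%, the true residual is 33% of the volume, so B has a diameter of 30 × 0.33^(1/3) = 20.7 mm. Over-reading it by 1.5 mm gives 22.2 mm and a residual of (22.2/30)³, about 40.7%. The result falls from 67% to 59.3%, a loss of 7.7 points. The same error in A moves it by 4.5.

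**Effect on the test at 121/61/61 with no true difference.** This is the chance of at least one false rejection when a lean favours both 19 G arms. The first figure uses the plan's SDs; the second uses an SD of 15.29 in every arm.
- No lean: 0.044 or 0.049
- 3 points: 0.41 or 0.34
- 10 points: above 0.99 in both cases

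**The case against.** The strongest reply is that nothing in the documents shows a needle-specific lean. Randomisation is blocked within centre, so a centre's habit of reading large or small is balanced across arms. If a reader overstates A and B by the same percentage, (A−B)/A does not change. This stands: only an arm-dependent lean matters, and its size is unknown.

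Several stronger readings are tempting, and the documents do not support them.
- A reader might infer that an unmasked operator takes the measurement. Section 8.3.1 names no reader, and neither document describes the trial as open-label. Both are plausible inferences from silence.
- A reader might take one range, such as 3 to 10 points, as the effect of a 1.5 mm lean. That would merge two formulas that move in opposite directions, and it depends on a cyst size that the documents do not give.
- A reader might conclude that a 1.5 mm lean equals the planned effect. At 30 mm that is roughly true of the protocol ratio (9.1 to 10.5 points for over-reading), but over-reading moves the SAP percentage by less than half of 10.
- A reader might regard A as the only subjective element. Under the SAP formula B is also a reading, taken after the needle has been used. Under the protocol wording, Protocol 7.2 leaves repositioning and repuncture partly to the operator.
- A reader might say that the reading can never be checked. SAP 3.1.1 presupposes pre- and post-procedure images, and B.12 guarantees access to source documents. The narrower point stands: the protocol requires only one saved image, does not say when it is taken, and plans no masked reading of it.

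**Conclusion.** The point holds as a finding about timing and missing masking. The denominator of the primary endpoint is read after assignment, under both definitions, with no protection described. Whether a lean will occur, and how large it would be, cannot be known from the documents. The illustrations rest on three assumptions: a lean of 1.5 mm, its presence in one arm only, and a spherical volume from the long axis. Under those, for cysts of 13 to 40 mm and true means of 67% or 77%, the shift is about 7 to 34 points for the protocol ratio and 2 to 15 for the SAP percentage. Even the lower part of these ranges matters against a 10-point design difference.

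The remedy protects A only. Under the SAP formula B is the larger exposure at 30 mm and 67%, and reordering does not touch it. This is an inexpensive improvement worth making; it is not evidence that the primary result will be biased.

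**What to change.** 1. In Protocol 8.2.4, 8.3.1 and Figure 3, and in the follow-up schedules of the Protocol Synopsis and SAP section 1, have the IWRS release the needle only after the long and short axes (of the largest locule if multilocular) are entered and time-stamped.
2. Conform the enrolment text (Protocol 8.2.2), the ITT definition and the note on exclusion criterion 1 (Protocol 9.3, SAP 4.1).
3. Replace the single saved image with two caliper images: one before the first puncture, and one at the end of the assigned needle's attempt and before any salvage. A and B can then be verified.
4. Reconcile the endpoint in Protocol 4.1 with the formula in SAP 3.1.1. If the SAP formula is kept, state that B remains an unmasked reading.

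The cost is revised wording, an IWRS change, a short delay in the room and one extra still image. Stratification is not disturbed, because centre is known and lesion location is already recorded at baseline (8.2.3). The diameters are already collected, and needles of another type must already be at hand for salvage. No extra patients or procedures are needed.
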